Fatigue	No interference with activity	Some interference with activity	Significant; prevents daily activity	ER visit or hospitalization
Myalgia	No interference with activity	Some interference with activity	Significant; prevents daily activity	ER visit or hospitalization

Table 9.4 extracted from: Guidance for Industry, Toxicity Grading Scale for Healthy Adult and Adolescent Volunteers Enrolled in Preventive Vaccine Trials, U.S. Department of Health and Human Services, Food and Drug Administration, Center for Biologics Evaluation and Research, August 2016

Treatment of cardiovascular and neurologic adverse events

- Local anesthetic systemic toxicity
 - Treatment will be initiated as recommended as the American Society of Regional Anesthesia and Pain Medicine, according to the society's checklist

Treatment will include: transfer to intensive care unit setting if not already in intensive care unit, continuous hemodynamic monitoring for at least 24 hours, appropriate airway management with assistance from respiratory therapy and a critical care consultant as needed, cardiovascular stabilization and assistance from a critical care consultant as needed, administration of Lipid Emulsion therapy, as per ASRA checklist in Appendix, Neurology consult for any observed systemic

neurologic toxicity (including change in vision, mental status change, persistent headache, seizure), Cardiology consult for any arrhythmias that persist greater than 30 minutes, beyond initial appropriate medical treatment, or result in hypotension with systolic blood pressure < 80mmHg.

Every adverse event, whether or not thought to be related to study drug, will be recorded and entered into the Medidata Rave® Case Report Form database.

Any medical condition present prior to study enrollment should not be reported as an adverse event, unless the medical condition worsens in severity or seriousness during the study. In this case it may be reported as an adverse event at the discretion of the Investigator.

The Investigator will review each event and assess its severity and relationship to the study treatment.

Criteria for stopping the study early:

Because this is a small study, criteria for stopping the study will not be based on statistical analysis but rather on the occurrence of any of the following serious adverse events in any of the subjects randomized to receive the ropivacaine pumps:

During immediate peri-operative period after pump has been connected:

 A single serious adverse event of LAST requiring rescue medication, cardiac resuscitation, or transfer to the ICU.

During the 5 day period of ambulatory pump use:

 A single serious adverse event of catheter site infection requiring hospital admission.

 A single serious adverse event of LAST requiring hospital admission.

During the entire study period:

 A single serious adverse event of any life-threatening adverse event deemed possibly related to the use of the ropivacaine pump.

 Two subjects receiving pumps experiencing moderate adverse events of tinnitus and/or metallic taste in the mouth.

11. Data Safety monitoring plan and/or DSMB:

As discussed in section 6, the medical monitor, [name], will review subject's research data and adverse events to ensure patient safety.”

12. Data Analysis:

The primary outcome measure is SEFAS scores at the indicated time points. A secondary outcome measure is use of opioids in the immediate postoperative period.

Each SEFAS response has 5 ordinal response choices scored 0 through 4, with the lowest score (0) representing the most severe disability and the highest total score being 48. If subjects omit a question the score will be re-normalized; however, the Redcap interface will be designed to try to obtain an answer for each question. The Mann-Whitney test will be used to examine differences in the SEFAS scores at each time point. For analysis of SEFAS scores, the pilot study sample size of 20 per group is sufficient for detecting a difference in scores between groups of 9 points with a power of 0.8 and $\alpha = 0.05$ (using the standard deviation obtained from SEFAS use in an ankle surgery study[35]); this score would represent moving up one rank in 3/4 of the questions which would be a functionally meaningful improvement given the 0 – 4 ordinal scale employed. . Patients who are withdrawn from the study due to failure of the initial nerve block (see above) will be considered as screening failures; no follow-up data or questionnaire scores will be obtained. We consider that such a failure is unlikely to have any relationship to the chronic pain outcome we are studying. The same approach will be taken for patients who decide to withdraw from the study, or are withdrawn by the attending surgeon or anesthesiologist, after randomization but before the single shot nerve block procedure.

Patients lost to follow-up after the end of the 5 day nerve block will be analyzed with a per-protocol analysis. We consider that, since the follow-up begins after the end of the treatment and consists only of completing questionnaires, there is unlikely to be a bias towards the experimental or control group having increased numbers of drop-outs.

Patients who have to (or choose to) remove the pump before the entire 5 day treatment period will also be analyzed both an intent-to-treat analysis and a per-protocol analysis. The duration of pump use will be noted.

As this is a pilot study, one intent is to develop estimates of the likelihood of drop-outs and incomplete treatments, to aid in design of a full sized study.

13. Data storage and confidentiality (include sample storage if applicable)

The signed consent forms will be stored in locked cabinets at the Westchester or UCMC locations, accessible only to the study members who are qualified to obtain consents. A single subject log (copy attached) will be kept by the study coordinator for matching patient study number, names, medical record number,

and surgery date. Study numbers will be used to identify questionnaire and clinical demographic data. As noted above, SEFAS data will be entered in the REDCap system, which provides password-protected security and encryption.

All other data will be entered into the Medidata Rave® database, and SEFAS data will be exported from REDCap and merged with the Medidata Rave® data for analysis. The Data Management Center (DMC) will provide full data management support to the project. The DMC has dedicated space within the Division of Biostatistics and Epidemiology (DBE) within Cincinnati Children's Hospital Me. The DMC currently consists of three Managers of Data Management operations and 25+ staff members (Clinical Research Data Specialists, Clinical Research Database Programmers and Data Coordinators), five of which are Certified Clinical Data Managers. DMC staff are active members of the Society of Clinical Data Management, the Drug Information Association, and the Society of Clinical Trials and subscribe to Good Clinical Data Management Practices.

Neither Medidata Rave® nor REDCap databases will contain subject names. The subject's enrollment into the study will be noted in the Epic chart, including a notation about whether or not they received the 5 day pumps, so that treating physicians will be aware of this history. Only authorized study personnel will have access to the rest of the data. In response to our query, the REDCap staff indicated that the REDCap system was not the best tool for conducting some of the types of analysis proposed (such as Mann-Whitney). A subset of the data (at least 20%) will be verified for accuracy by the study monitor. Files exported from Medidata Rave® that are generated for analysis of the de-identified data will be stored on the research server. This College of Medicine server is password protected so that only members of the Research Director's laboratory can have access, and the directory containing study data will be further restricted so only the researchers directly involved in the study have access. The server contents are automatically backed up several times per day and retained off-site for 30 days.

Once the study has been completed, the subject log will be destroyed and only the de-identified electronic data will be kept. Only study personnel will have access to the de-identified data except as required for regulatory oversight.

14. Study Population (Including age, number of individuals, inclusion/exclusion)

Sample Size - Up to 60 patients will be enrolled in this single site pilot study.

Inclusion criteria –

- Adult patients of either sex, age 18 to 65
- Referred for surgery for open reduction and internal fixation for ankle fracture

- Agreed to have a single shot local nerve blockade (routinely offered as part of the standard-of-care but declined by some patients)

Exclusion criteria:

- patients unable to give informed consent in English
- unable to complete surveys in English
- unable to understand instructions for using the pump in English
- unavailable for follow-up
- Scheduled to enter a rehabilitation facility after the surgery (due to difficulty in conducting the 5 days of safety monitoring phone calls)
- polytrauma, i.e. undergoing other surgeries or having other fractures related to the precipitating cause of the ankle fracture
- infection such as abcess or bacterial infection; mild colds or upper respiratory infections do not require exclusion.
- peripheral vascular disease
- diabetes
- undergoing chemotherapy
- pregnancy (ropivacaine is FDA pregnancy category B; pregnancy test is routine part of the surgical procedure unless the woman signs a waiver; patients who sign such a waiver instead of having a pregnancy test will not be eligible for the study, unless their medical record clearly indicates they have had a hysterectomy or tubal ligation.)
- lactating
- have heart disease or heart rhythm disorder or taking anti- antiarrhythmic drugs
- severe renal impairment (Class 3 or worse kidney disease)
- liver disease (cirrhosis or liver failure)
- ever had an allergic reaction to any type of local anesthetic
- taking therapeutic doses of anti-coagulants or anti-platelet therapy (prophylactic doses started because of the hospital admission are not an exclusion)
- taking antidepressants or other psychiatric medications (due to drug interaction risk per the ropivacaine data sheet)
- single shot local nerve block prior to surgery was ineffective (rare; see below)
- selected for neuraxial anesthesia rather than general anesthesia for the open reduction surgery (rare)
- already receiving chronic analgesic therapy for a separate chronic pain condition

Rarely, the single shot local nerve blockade given prior to surgery as standard-of-care is found to be ineffective, and surgery proceeds using only general anesthesia. The ineffectiveness of the single shot would indicate that the catheter placement was also likely to be ineffective. For such patients, the

catheter will be removed before the surgery and they will be removed from the study; attempting to re-position and re-test the catheter outside of the standard-of-care procedures was deemed to be undue risk. Patients with failed nerve block who were not randomized to receive the pump will also be removed to avoid bias in the analysis, and because the lack of the single nerve block might also have effects on the development of chronic pain.

Because the treatment period lasts only 5 days, patients who may possibly become pregnant during that time are allowed to participate.

15. Consenting process and plan

A typical schedule for the potential subjects is for them to be admitted to the emergency department, diagnosed with ankle fracture, then either admitted to the hospital or sent home, after being scheduled for surgery for open reduction and internal fixation of the fracture the next day. In order to identify potential subjects, the study coordinator or others listed on the IRB protocol who have Epic privileges will review the orthopedic surgery schedules at the participating hospitals to identify potential subjects. We have applied for an IRB waiver to do a preliminary research screening in the medical record to avoid approaching potential subjects outside the age range or with polytrauma or other excluded conditions. A paper prescreening form will be used, listing inclusion and exclusion criteria, to determine as far as possible from the medical chart of scheduled patients whether the patient is eligible. If the patient agrees to join the study, this document will be kept with the consent form; if not, the document will be used to document the reason for the screening failure or to note that the patient refused to participate. The form will then be shredded; the sex, age in years, and reason for not enrolling in the study will be the only data retained. The orthopedic surgeon and the anesthesiologist scheduled to conduct the surgery will be contacted to confirm that they are willing to have the patient enrolled in the study, before subjects are enrolled. We will introduce the study to both the Anesthesiology and Orthopedic Surgery departments prior to the beginning of the study. Patients who have passed the prescreening and who will come to the surgery after hospital admission will be contacted in their rooms to invite them to participate, prior to the scheduled surgery (but after patients have been admitted to the hospital from the emergency room if that is where they initially presented). Patients who are scheduled to come to the surgery from home will be contacted at home by telephone, if they have passed the prescreening. In both cases patients will be requested to arrive at least 30 minutes earlier than otherwise scheduled so that consent and enrollment can be done in the pre-operative period. Consent will be obtained before the anesthesiologist starts the standard-of-care nerve block procedure.

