There are no additives in the final ropivacaine 800 mL bag that would affect stability beyond that of the commercial product. In order to ensure the sterility of the ropivacaine during the 5 days of use, the following procedure will be used: The final ropivacaine 800 mL bags will be considered medium-risk compounded sterile products (CSP). In lieu of a separate sterility test, USP 797 guidance indicates medium-risk CSPs should have a beyond use date (BUD) of 30 hours when stored at room temperature. To extend the BUD, sterility testing will be performed on each batch of ropivacaine 800 mL bags. Two of the bags in each batch will be tested for sterility using the QT JuniorTM System (Q.I. Medical, Inc., Grass Valley, CA, USA), which utilizes a 0.22-micron filtration set and fluid thioglycollate growth media [22]. The batched bags will remain quarantined before use for 14 days after preparation. On day 14, the QT systems being incubated from the 2 tested bags will be visually inspected for turbidity per the manufacturer instructions. If no turbidity is seen (i.e., negative growth) at day 14, then the batched bags will be released for dispensing for an additional 14 days (i.e., 28 days total from preparation: 14 days quarantined plus 14 days post-release) while being stored at controlled room temperature in the investigational pharmacy until dispensed or expired. Released bags will only be dispensed if the BUD does not extend beyond the planned 5-day therapy for a specific patient. Following the patient-specific dispense, the ropivacaine bag and pump will be connected directly to the nerve block catheter at the time the catheter is inserted, in the same day surgery area immediately after the single popliteal nerve block is administered. The catheter will be infused using a commercially available ambulatory infusion pump consistent with standard clinical care. Infusion will begin immediately after the surgery, when the patient is in the PACU.

Subjects will be contacted by phone each day by the study nurse or other clinical study member. The script to be used for this follow-up is provided in a separate document. This allows monitoring for post-operative analgesic use, toxicity, infection, or other problems related to the use of the pump, and for reminders about when and how to remove the catheter.

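### The bag-dispensing rule is worded backwards: read literally, it allows only bags that reach their beyond-use date by the end of the 5-day infusion

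*Protocol*

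**What the plan says.** The text is in Protocol section 6 (Study design), in the paragraph on stability and sterility of the compounded 800 mL bags. The procedure is introduced by its purpose: "In order to ensure the sterility of the ropivacaine during the 5 days of use, the following procedure will be used". The paragraph notes that, without a separate sterility test, "medium-risk CSPs should have a beyond use date (BUD) of 30 hours when stored at room temperature"; each batch is tested so that a longer date can be used.

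The timetable follows. "The batched bags will remain quarantined before use for 14 days after preparation". If no growth is seen on day 14, the bags are "released for dispensing for an additional 14 days", which the text spells out as "28 days total from preparation: 14 days quarantined plus 14 days post-release". Meanwhile they are "stored at controlled room temperature in the investigational pharmacy until dispensed or expired".

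Then comes the condition that links a bag's date to a patient's treatment: "Released bags will only be dispensed if the BUD does not extend beyond the planned 5-day therapy for a specific patient". After dispensing, "the ropivacaine bag and pump will be connected directly to the nerve block catheter at the time the catheter is inserted", and the infusion starts in the recovery unit straight after surgery.

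No other sentence in the protocol restates this condition, and the SAP does not deal with bag dating.

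**The concern.** The sentence tests whether the BUD runs past the therapy. The question that matters for sterility is whether the therapy runs past the BUD. With the two terms swapped, the rule selects bags that reach or pass their date by the end of the infusion and rejects bags that would stay in date throughout. That defeats the purpose given at the head of the same procedure.

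This is an operative release criterion. The bags are pooled from preservative-free product, kept at room temperature and infused at home. Section 10 makes a single serious catheter-site infection needing admission during pump use a reason to stop the study. It also has monitors check conduct against the approved protocol; on this point the text gives them the wrong standard. Taken at its word, the sentence makes correct dispensing of a fresh bag a deviation, while a bag that expires during the infusion meets the stated condition.

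**Working it through.** **Inputs** (all from Protocol section 6)

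- Quarantine: 14 days after preparation.
- Further release period: 14 days.
- Planned therapy: 5 days from one bag.
- Start of infusion: the bag is connected when the catheter is placed and the infusion begins after surgery, so the start is taken as the day of dispensing.

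**The plan's own figure.** 14 + 14 = 28 days from preparation, which reproduces the stated total. The text does not say outright that the BUD is day 28; this is read from the 28-day total and from bags being kept until they expire.

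**The two rules.** Let *d* be the dispensing day after preparation, from 14 to 28. Counting both end dates gives 28 − 14 + 1 = 15 dates. The infusion ends on day *d* + 5.

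- As written (BUD no later than end of therapy): 28 ≤ *d* + 5, so *d* ≥ 23.
- As evidently intended (end of therapy no later than BUD): *d* + 5 ≤ 28, so *d* ≤ 23.
- Overrun past the BUD: (*d* + 5) − 28 days, when positive.

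| | As written | Intended |
|---|---|---|
| Dates allowed | 23 to 28 (6) | 14 to 23 (10) |
| Dates barred | 14 to 22 (9) | 24 to 28 (5) |
| Overrun on allowed dates | 0, 1, 2, 3, 4, 5 days | none |

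The rules agree on day 23 only, when the infusion ends exactly on day 28. On 5 of the 6 dates allowed by the wording, the infusion runs past the BUD.

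**Sensitivity**

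- *Infusion starts the day after dispensing.* The end day is *d* + 6. As written: *d* ≥ 22 (7 dates, overrun 0 to 6 days). Intended: *d* ≤ 22 (9 dates). They agree on day 22 only.
- *Day 14 not counted as a dispensing date.* The window has 14 dates. The wording then bars 8 dates (15 to 22) and the intended rule allows 9 (15 to 23). Nothing else changes.
- *Another BUD.* For a BUD on day *B*, the wording requires *d* ≥ *B* − 5 and the intent requires *d* ≤ *B* − 5. The rules meet at one date at most, so the inversion does not depend on day 28.

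**The case against.** The strongest reply is that nobody would follow the literal words. The purpose is stated in the same paragraph, the bags are prepared and dispensed by qualified pharmacy staff under recognised compounding standards, and the ordinary meaning of a beyond-use date excludes infusing past it. Read as a whole, the protocol does not authorise out-of-date infusion; on this view one sentence clashes with its surroundings and needs only an editorial correction. This largely stands as a statement about practical risk. It does not make the sentence right, and no correct statement of the rule exists elsewhere to fall back on.

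A second reply is that conflict with the 14-day release period proves little, because the correct rule also shortens that period. This is fair: the intended rule removes 5 of the 15 dates and the literal one removes 9. The difference that counts is which dates go. The intended rule drops the oldest bags and the literal rule drops the freshest.

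A third reply is that day 28 and the 15-date count are inferences. They are, and the counts should be read that way. The reversal itself does not rest on them.

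**Conclusion.** The concern holds. The dispensing condition is the reverse of what the paragraph sets out to secure, probably through a drafting slip. With the BUD taken as day 28, whole-day counting and a same-day start, the wording allows days 23 to 28 with up to 5 days of infusion past the BUD, and bars days 14 to 22, when a bag would stay in date throughout.

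The practical risk is modest. If the pharmacy applies the intended rule, no patient is affected. The documents give no infection rate for use past the BUD, so no added patient risk can be put in figures. Sample size, endpoints and statistical analysis are unaffected. The sentence should still be corrected, because it is a safety rule that gives the wrong result when followed exactly.

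**What to change.** Reverse the condition in Protocol section 6. Suggested wording: *A released bag may be dispensed for a patient only if that patient's planned 5-day infusion will finish on or before the bag's BUD.* It would help to state the BUD explicitly as day 28 after preparation, if that is what is meant, and to add that with a same-day start the last dispensing date is day 23 (28 − 5). If the pharmacy works from a separate procedure, which is not among these documents, it should carry the same wording.

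The cost is one protocol sentence and any matching pharmacy text. No extra testing, staff or patients are needed.

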The treatment will be open label due to the impracticality of blinding the physician or patient to the presence of local anesthetic in the 5 – day pump and the ethical barriers to subjecting patients to implantation of a catheter and empty or saline pump with no benefit to them. Per standard of care, patients in both the

experimental and control groups will also have other oral pain medications prescribed for use as needed.

Additional data routinely obtained for clinical purposes will also be collected including demographic variables, opioid use in the PACU, pain medications prescribed at discharge, and type of ankle fracture. Standard database templates will be used to record information from the medical record where appropriate.

The patients randomized to the 5 day pump group will be undergoing an experimental procedure: ambulatory pumps for peripheral nerve block (including popliteal) are already successfully used in our clinics (with patients taking the pumps home and doing the removal of the catheter there) in the context other surgeries; but this is not routinely done for ankle fracture surgery nor for the indication of preventing development of chronic pain. In addition, normally the pumps are used for a shorter period of time.

The standard follow-up appointments with the orthopedic surgeons following ankle surgeries are at 10 - 14 days, 5 – 6 weeks, and 3 – 4 months. These visits will allow for monitoring of unexpected problems in patients receiving the pumps. In order to have consistent monitoring, a single orthopedic doctor will review the charts of all the enrolled patients in the experimental group on a regularly scheduled basis (at least monthly). As per our grant proposal patient charts will be reviewed for up to 3 months after use of the pumps. In addition, [name] will act as medical monitor for the study. He will review subject's research data and adverse events to ensure patient safety. The medical monitor will have the power to temporarily or permanently halt enrollment, if it is deemed that patient safety is compromised.

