PACU and recorded in the electronic record, until the patient is discharged from the PACU. Chart review of the follow-up orthopedic appointments will be used to identify possible development of chronic pain conditions or unforeseen complications of 5 day pump use.

8. Specimen collection: not applicable.

9. Potential Benefits:

Possible benefits to the subject during the time the pump is in use include better postoperative pain control, improved sleep, and reduced need for opioids with their concomitant side effects and risk of abuse [26]. Preclinical data (see above) and some clinical data in other conditions provide some support for the hypothesis being tested that the nerve block will reduce the risk of chronic pain [27]. If this pilot study is successful and can be extended to a full study large enough to fully test this hypothesis, the research may contribute generalizable knowledge to improve practices in combat medicine and trauma medicine.

10. Potential Risks, Discomforts, and inconveniences:

Level of risk: Greater than minimal risk

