## I. Mock tables to be produced

Table 1: Descriptive table of demographics of experimental and control groups prior to intervention.

Description	Control (N = ***) 	Experimental (N = ***) 	p value
Age at ankle surgery (years)			
Weight at time of surgery			
Height at time of surgery			
BMI at time of surgery			
Race			
Ethnicity			
Ankle fracture: number of malleoli affected			
Grade of injury (defined as closed injury, or open injury with Gustilo Anderson classification grade 1, grade 2, grade 3a, grade 3b, grade 3cr) 			
Time in surgery			
Estimated blood lost in surgery			
Number of plates implanted			
Total length of plates implanted			
Total number of screw holes in implanted hardware			

Mean, SD, median, interquartile range for continuous variables, number and % per group for categorical variables.

 Converted to ordinal scale 1 – 6

Table 2 Pain outcomes

Description	Control (N = ***)	Experimental (N = ***)	p value
Opioid medication use in PACU: analgesic equivalents			
Time in PACU			
PACU discharge status (home, rehab facility, hospital) 			
PACU Pain score AUC			

Average Pain score in PACU			
SEFAS score (2 week)			
Pain medication use analgesic equivalents (2 week)			
SEFAS score (3 month)			
Pain medication use analgesic equivalents (3 month)			
SEFAS score (6 month)			
Pain medication use analgesic equivalents (6 month)			
SEFAS score (12 month)			
Pain medication use analgesic equivalents (12 month)			
Number (%) with any chronic pain diagnosis at 12 months			

 Converted to ordinal scale 1 – 3

Table 3 Other outcomes

Description	Control (N = ***)	Experimental (N = ***)	p value
Number (%) requiring re-operation			
Number (%) : Indication for re-operation (infection, non-union, hardware failure, hardware removal, other)			
Wound healing status at first FU (dehiscence, cellulitis , deep infection, healing well, other) 			
Wound healing status at second FU (dehiscence, cellulitis , deep infection, healing well, other) 			
Weight bearing current status at first FU [full, assisted (cane, walker, boot), non (crutch)] 			
Weight bearing current status at second FU [full, assisted			

(cane, walker, boot), non (crutch)] 			
---	--	--	--

 Converted to ordinal scale

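### The scheduled monthly chart review covers the pump arm only, so adverse events and milder complications are sought more systematically there than in controls

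*Protocol*

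**What the plan says.** Protocol section 6 (Study design) introduces the three standard orthopedic appointments and says "These visits will allow for monitoring of unexpected problems in patients receiving the pumps". For consistency, one orthopedic doctor then "will review the charts of all the enrolled patients in the experimental group on a regularly scheduled basis (at least monthly". The duration follows: "As per our grant proposal patient charts will be reviewed for up to 3 months after use of the pumps". Both the group reviewed and the clock are thus defined by the pump. The same section states "The treatment will be open label due to the impracticality of blinding the physician or patient" and describes no blinded chart reviewer.

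Other text on finding problems:

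- **Daily telephone contact (Protocol section 6).** It refers to subjects without naming an arm, but its purpose is put in pump terms: "This allows monitoring for post-operative analgesic use, toxicity, infection, or other problems related to the use of the pump".
- **Chart review of follow-up appointments (Protocol section 7).** No arm is named. The aim is to "identify possible development of chronic pain conditions or unforeseen complications of 5 day pump use".
- **Adverse event recording (Protocol section 10).** "Every adverse event, whether or not thought to be related to study drug, will be recorded". This covers both arms, but no schedule for finding events in controls is given.
- **Medical monitor (Protocol sections 6 and 11).** Reviews research data and adverse events, with no limit by arm.
- **SAP sections C, E and G.** Clinical variables are extracted by chart review, with no limit by arm.
- **SAP section I, Table 3.** Compares the arms, with a p value column, on items that include "Number (%) requiring re-operation", wound healing and weight bearing.

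**The concern.** A complication count depends on how often events occur and on how hard they are looked for. Here a named reviewer reads pump-arm charts on a schedule with complications in mind, and control charts get no such reading. Neither patients nor physicians are blinded, so nothing in the design offsets the difference. A mild event written into a chart between appointments is more likely to reach the adverse event database if the patient had a pump.

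Screening for potential problems is part of the second aim in Protocol section 4, and section 12 says that one intent of the pilot is to help design a full-sized study. An excess of minor events in the pump arm that was partly due to closer looking could mislead that planning.

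**Working it through.** The plan states no figure on this point, so there is none to reproduce. The check is a reading of each outcome against the way it is captured, followed by an illustration.

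**Step 1: which outcomes depend on the pump-arm review?**

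| Outcome | How it is captured | Exposure |
|---|---|---|
| SEFAS | Patient questionnaire, both arms | None from this review |
| PACU pain and opioid use | PACU record, both arms | None |
| Stopping criteria (Protocol section 10) | Defined for pump subjects only | None; no control rate is needed |
| Wound healing, weight bearing (Table 3) | Status at first and second follow-up visit | Little |
| Chronic pain diagnosis at 12 months (Table 2) | One-year follow-up (SAP section E) | Little; the review ends at about 3 months |
| Re-operation (Table 3) | Chart; not tied to a visit in SAP section E | Slight; an operation would be charted in either arm |
| Adverse events, milder charted complications | Recorded when found; scheduled search in the pump arm only | Yes |

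Catheter-site events cannot occur in controls, so the issue concerns events that either arm can have.

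**Step 2: how large could the distortion be?** Inputs: 20 per group (Protocol section 12), a true risk p that is equal in both arms (assumed), and control detection s relative to the pump arm (assumed). With full detection in the pump arm:

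- expected events found: 20 × p (pump) and 20 × p × s (control)
- apparent risk ratio: 20p / (20ps) = 1/s
- chance that more events are found in the pump arm: P(X > Y), with X ~ Binomial(20, p) and Y ~ Binomial(20, ps), independent

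| p | s | Found, pump | Found, control | Apparent ratio | P(more in pump arm) |
|---|---|---|---|---|---|
| 5% | 1.0 | 1.0 | 1.0 | 1.00 | 0.345 |
| 5% | 0.8 | 1.0 | 0.8 | 1.25 | 0.392 |
| 5% | 0.6 | 1.0 | 0.6 | 1.67 | 0.445 |
| 5% | 0.4 | 1.0 | 0.4 | 2.50 | 0.504 |
| 10% | 1.0 | 2.0 | 2.0 | 1.00 | 0.393 |
| 10% | 0.8 | 2.0 | 1.6 | 1.25 | 0.474 |
| 10% | 0.6 | 2.0 | 1.2 | 1.67 | 0.565 |
| 10% | 0.4 | 2.0 | 0.8 | 2.50 | 0.665 |
| 20% | 1.0 | 4.0 | 4.0 | 1.00 | 0.421 |
| 20% | 0.8 | 4.0 | 3.2 | 1.25 | 0.549 |
| 20% | 0.6 | 4.0 | 2.4 | 1.67 | 0.684 |
| 20% | 0.4 | 4.0 | 1.6 | 2.50 | 0.813 |

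In counts the effect is small. At s = 0.6 the gap is 2.0 − 1.2 = 0.8 events when p = 10%, and 4.0 − 2.4 = 1.6 events when p = 20%. One event is 1/20 = 5 percentage points of an arm.

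**Step 3: cost of equal review.** Controls number 40/2 = 20 (evaluable) to 60/2 = 30 (maximum enrolled). Three monthly reviews each gives 20 × 3 = 60 to 30 × 3 = 90.

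**The case against.** The strongest reply is that the extra activity is only chart reading. It adds no visit, examination or patient contact, so it can surface only what is already written down. The SAP draws on the same charts for both arms. A reader might infer that events between visits can be found in the pump arm alone. The documents do not support that, because a charted control event remains available to the extraction. What stands is narrower: SAP section C ties its extraction to the follow-up appointments, and only the pump arm has a scheduled reading beyond that.

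Second, a reader might infer that Table 3 is biased. Its wound and weight-bearing items are statuses at fixed visits, and a re-operation is hard to miss in any chart. No text says that the monthly review feeds Table 3. Equally, none says that its findings are kept out of the compared data.

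Third, the SAP contains no adverse event table or test, so no formal comparison of adverse events is planned. This is correct and limits the consequence. It does not change the fact that events in both arms go into one database under unequal search.

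Fourth, closer watching of the arm that receives an experimental procedure is a reasonable safeguard. Agreed. The difficulty arises only when the arms are compared.

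Fifth, 20 per group says little about rare complications even with perfect ascertainment. Protocol section 10 cites 3 complications in 290 popliteal catheters and local infection of 0 to 3%. At a 3% risk, 20 × 0.03 = 0.6 events are expected per arm, and 0.6 × 0.6 = 0.36 would be found in controls if s = 0.6. Small numbers are therefore the main limit on a safety contrast, and the unequal search is an avoidable addition to it.

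**Conclusion.** The point holds as a limited asymmetry in ascertainment. The monthly review and its window are restricted to the pump arm, and no section provides a counterpart for controls. Adverse events and milder charted complications, especially those noted outside the standard visits, are looked for more systematically with the pump. Any between-arm contrast of them would tend to overstate pump harm.

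The size cannot be derived from the documents. The ratios of 1.25 to 2.5 rest wholly on assumed relative detection of 80% to 40% and on equal true risks. They should not be read as estimates, and low detection is implausible for a re-operation. It would also go too far to infer that the primary result is compromised, or that this asymmetry is what prevents the pilot from settling whether the pump adds complications. SEFAS does not pass through the review, and the small sample limits the safety inference in any case. This is a cheap improvement to the plan.

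**What to change.** Amend Protocol section 6 so that the scheduled chart review covers every enrolled patient in both randomised groups, with the same reviewer, frequency and form. Time the three-month window from surgery in both arms, because controls have no pump use to count from.

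If the review stays limited to the pump arm, add to the SAP that comparisons of complications and adverse events between arms use only data collected identically in both, and that findings from the pump-arm review are reported separately. In either case, state which arm receives the daily telephone contact, since equal chart review alone does not settle that source.

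The full change costs roughly 60 to 90 additional short chart reviews by the existing reviewer, with no extra staff or patient contact. Protocol section 6 says that the consent form already allows record access for complications. The minimum change costs a sentence or two in the SAP.
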